#### **5.3.5.4 Abnormal Laboratory Values**

Not every laboratory abnormality qualifies as an AE. A laboratory test result must be reported as an AE if it meets any of the following criteria:

- Is accompanied by clinical symptoms
- Results in a change in study treatment (e.g., dosage modification, treatment interruption, or treatment discontinuation)
- Results in a medical intervention (e.g., potassium supplementation for hypokalemia) or a change in concomitant therapy
- Is clinically significant in the Investigator's judgment

Note: For oncology trials, certain abnormal values may not qualify as AEs.

It is the Investigator's responsibility to review all laboratory findings. Medical and scientific judgment should be exercised in deciding whether an isolated laboratory abnormality should be classified as an AE.

If a clinically significant laboratory abnormality is a sign of a disease or syndrome (e.g., alkaline phosphatase and bilirubin  $5 \times$  ULN associated with cholestasis), only the diagnosis (i.e., cholestasis) should be recorded on the eCRF.

If a clinically significant laboratory abnormality is not a sign of a disease or syndrome, the abnormality itself should be recorded on the eCRF, along with a descriptor indicating whether the test result is above or below the normal range (e.g., "elevated potassium," as opposed to "abnormal potassium"). If the laboratory abnormality can be characterized by a precise clinical term per standard definitions, the clinical term should be recorded as the AE. For example, an elevated serum potassium level of 7.0 mEq/L should be recorded as "hyperkalemia."

Observations of the same clinically significant laboratory abnormality from visit to visit should only be recorded once on the eCRF (see Section 5.3.5.4 for details on recording persistent AEs).

### **5.3.5.5      Abnormal Vital Sign Values**

Not every vital sign abnormality qualifies as an AE. A vital sign result must be reported as an AE if it meets any of the following criteria:

- Is accompanied by clinical symptoms
- Results in a change in study treatment (e.g., dosage modification, treatment interruption, or treatment discontinuation)
- Results in a medical intervention or a change in concomitant therapy
- Is clinically significant in the Investigator's judgment

It is the Investigator's responsibility to review all vital sign findings. Medical and scientific judgment should be exercised in deciding whether an isolated vital sign abnormality should be classified as an AE.

If a clinically significant vital sign abnormality is a sign of a disease or syndrome (e.g., high blood pressure), only the diagnosis (i.e., hypertension) should be recorded on the eCRF.

Observations of the same clinically significant vital sign abnormality from visit to visit should only be recorded once on the eCRF (see Section [5.3.5.4](#) for details on recording persistent AEs).

### **5.3.5.6      Abnormal Liver Function Tests**

The finding of an elevated ALT or AST ( $>3 \times$  baseline value) in combination with either an elevated total bilirubin ( $>2 \times$  ULN) or clinical jaundice in the absence of cholestasis or other causes of hyperbilirubinemia is considered to be an indicator of severe liver injury (as defined by Hy's Law). Therefore, Investigators must report as an AE the occurrence of either of the following:

- Treatment-emergent ALT or AST  $>3 \times$  baseline value in combination with total bilirubin  $>2 \times$  ULN (of which  $\geq 35\%$  is direct bilirubin)
- Treatment-emergent ALT or AST  $>3 \times$  baseline value in combination with clinical jaundice

The most appropriate diagnosis or (if a diagnosis cannot be established) the abnormal laboratory values should be recorded on the eCRF (see Section [5.3.5.2](#)) and reported to the Sponsor immediately (i.e., no more than 24 hours after learning of the event), either as a serious AE or an AE of special interest (see Section [5.4.2](#)).

### **5.3.5.7      Deaths**

All deaths that occur during the protocol-specified AE reporting period (see Section [5.3.1](#)), regardless of relationship to study drug, must be recorded on the eCRF and immediately reported to the Sponsor (see Section [5.4.2](#)). This includes death attributed to progression of hepatic disease.

Death should be considered an outcome and not a distinct event. The event or condition that caused or contributed to the fatal outcome should be recorded as the single medical concept on the eCRF. Generally, only one such event should be reported. If the cause of death is unknown and cannot be ascertained at the time of reporting, "**unexplained death**" should be recorded on the eCRF. If the cause of death later becomes available (e.g., after autopsy), "unexplained death" should be replaced by the established cause of death. The term "**sudden death**" should not be used unless combined with the presumed cause of death (e.g., "sudden cardiac death").

If the death is attributed to progression of liver disease, "hepatic disease progression" should be recorded on the eCRF.

Deaths that occur after the AE reporting period should be reported as described in Section [5.6](#).

#### **5.3.5.8 Pre-existing Medical Conditions**

A preexisting medical condition is one that is present at the screening visit for this study. Such conditions should be recorded on the eCRF.

A preexisting medical condition should be recorded as an AE only if the frequency, severity, or character of the condition worsens during the study. When recording such events on the eCRF, it is important to convey the concept that the preexisting condition has changed by including applicable descriptors (e.g., "more frequent headaches").

#### **5.3.5.9 Worsening of Liver Disease**

Medical occurrences or symptoms of deterioration that are anticipated as part of liver disease should be recorded as an AE if judged by the Investigator to have unexpectedly worsened in severity or frequency or changed in nature at any time during the study. When recording an unanticipated worsening of hepatic function on the eCRF, it is important to convey the concept that the condition has changed by including applicable descriptors (e.g., "accelerated worsening of hepatic function").

#### **5.3.5.10 Hospitalization or Prolonged Hospitalization**

Any AE that results in hospitalization (i.e., inpatient admission to a hospital) or prolonged hospitalization should be documented and reported as a serious AE (per the definition of serious AE in Section [5.2.2](#)), except as outlined below.

An event that leads to hospitalization under the following circumstances should not be reported as an AE or a serious AE:

- Hospitalization for respite care

- Hospitalization for a preexisting condition, provided that all of the following criteria are met:

The hospitalization was planned prior to the study or was scheduled during the study when elective surgery became necessary because of the expected normal progression of the disease

The patient has not experienced an AE

An event that leads to hospitalization under the following circumstances is not considered to be a serious AE, but should be reported as an AE instead:

- Hospitalization that was necessary because of patient requirement for outpatient care outside of normal outpatient clinic operating hours

#### **5.4 IMMEDIATE REPORTING REQUIREMENTS FROM INVESTIGATOR TO SPONSOR**

Certain events require immediate reporting to allow the Sponsor to take appropriate measures to address potential new risks in a clinical trial. The Investigator must report such events to the Sponsor immediately; under no circumstances should reporting take place more than 24 hours after the Investigator learns of the event. The following is a list of events that the Investigator must report to the Sponsor within 24 hours after learning of the event, regardless of relationship to study drug:

- Serious AEs (defined in Section 5.2.2; see Section 5.4.2 for details on reporting requirements)
- Adverse events of special interest (defined in Section 5.2.3; see Section 5.4.2 for details on reporting requirements)
- Pregnancies (see Section 5.4.3 for details on reporting requirements)
- Accidental overdoses or medication errors (see Section 5.4.4 for details on reporting requirements)

The Investigator must report new significant follow-up information for these events to the Sponsor immediately (i.e., no more than 24 hours after becoming aware of the information). New significant information includes the following:

- New signs or symptoms or a change in the diagnosis
- Significant new diagnostic test results
- Change in causality based on new information
- Change in the event's outcome, including recovery
- Additional narrative information on the clinical course of the event

Investigators must also comply with local requirements for reporting serious AEs to the local health authority and IRB/EC.

#### **5.4.2        Reporting Requirements for Serious Adverse Events and Adverse Events of Special Interest**

##### **5.4.2.1      Events That Occur prior to Study Drug Initiation**

After informed consent has been obtained but prior to initiation of study drug, only serious AEs caused by a protocol-mandated intervention should be reported. The paper Clinical Trial Serious Adverse Event/Adverse Event of Special Interest Reporting Form provided to Investigators should be completed and submitted to the Sponsor or its designee immediately (i.e., no more than 24 hours after learning of the event), either by faxing or by scanning and emailing the form using the fax number or email address provided to Investigators.

##### **5.4.2.2      Events That Occur after Study Drug Initiation**

After initiation of study drug, serious AEs and AEs of special interest will be reported until 28 days after the dose of study drug. Investigators should record all case details that can be gathered immediately (i.e., within 24 hours after learning of the event) on the eCRF and submit the report via the electronic data capture (EDC) system. An electronic report will be generated and sent to Roche Safety Risk Management.

In the event that the EDC system is unavailable, the paper Clinical Trial Serious Adverse Event/Adverse Event of Special Interest Reporting Form provided to Investigators should be completed and submitted to the Sponsor or its designee immediately (i.e., no more than 24 hours after learning of the event), either by faxing or by scanning and emailing the form using the fax number or email address provided to Investigators. Once the EDC system is available, all information will need to be entered and submitted via the EDC system.

Instructions for reporting serious AEs that occur >28 days after the dose of study treatment are provided in Section [5.6](#).

#### **5.4.3        Reporting Requirements for Pregnancies**

##### **5.4.3.1      Pregnancies in Female Patients**

Female volunteers of childbearing potential will be instructed to immediately inform the Investigator if they become pregnant during the study or within 28 days after the dose of study drug. A paper Clinical Trial Pregnancy Reporting Form should be completed and submitted to the Sponsor or its designee immediately (i.e., no more than 24 hours after learning of the pregnancy), either by faxing or by scanning and emailing the form using the fax number or email address provided to Investigators. Pregnancy should not be recorded on the eCRF. The Investigator should counsel the volunteer, discussing the

risks of the pregnancy and the possible effects on the fetus. Monitoring of the volunteer should continue until conclusion of the pregnancy. Any serious AEs associated with the pregnancy (e.g., an event in the fetus, an event in the mother during or after the pregnancy, or a congenital anomaly/birth defect in the child) should be reported on the eCRF. In addition, the Investigator will submit a Clinical Trial Pregnancy Reporting Form when updated information on the course and outcome of the pregnancy becomes available.

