## PROTOCOL AMENDMENT, VERSION 2: RATIONALE

Protocol GP41174 has been amended to update safety data to align with most recent Entrectinib Investigator's Brochure (Version 9, Addendum 1). Changes to the protocol, along with a rationale for each change, are summarized below:

- Inclusion of the safety risks has been added to list of less common risks for entrectinib and the information has been put in tabular form (Section 1.1.4):

Less Common (occurs in 1%–10% of patients)

• Difficulty swallowing

• Bone fracture

• Fainting due to drop in blood pressure

• Weakness of the heart muscle causing decreased pumping of blood, which may cause breathing difficulty, reduced kidney function, and fluid accumulation

• Electrocardiogram (ECG) QT prolonged, which may mean heart is not working normally

- The protocol has been updated to specify that women of child-bearing potential are required to remain abstinent or use a highly effective method of contraception throughout the study and for 5 weeks after last study treatment. Men with female partners of child-bearing potential must agree to remain abstinent or use barrier contraception throughout the study and for 3 months after the last study treatment. Men whose female partners are pregnant must also use barrier contraception throughout the study to avoid potential exposure of the fetus to the study drug (Sections 1.2.2 and 4.4.2).
- Information has been added to clarify that re-screening is not allowed (Section 3.1).
- Information about future use of screening samples has been added (Section 4.5.5).

Additional minor changes have been made to improve clarity and consistency. Substantive new information appears in italics. This amendment represents cumulative changes to the original protocol.

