### **1.2.2 Benefit-Risk Assessment**

There will be no therapeutic benefit for the volunteers participating in the study.

The risks of participation are primarily those associated with adverse reactions to the study drug, although there may also be some discomfort from collection of blood samples and other study procedures. The tolerability profile of entrectinib from administration of single doses up to 800 mg to healthy subjects has been characterized from previous clinical studies. There have been few AEs following entrectinib dosing in

previous clinical studies in healthy volunteers and no specific safety concerns have been identified about the use of 100 mg entrectinib in volunteers with impaired hepatic function in this study. Of the risks identified in the IB, none require specific monitoring or risk mitigation procedures. Potential drug-drug interactions with other medications are addressed by restrictions on concomitant medication use. Potential risks to a developing fetus from entrectinib exposure in utero are addressed by exclusion of pregnant females from the study and the requirement for all participants to use *highly effective* contraception throughout the study. *In addition, woman need to use highly effective contraception for 5 weeks after cessation of entrectinib treatment and men with female partners of childbearing potential or female partners who are pregnant need to use highly effective contraception for 3 months after last study treatment.*

Overall, no significant safety concerns have been identified about the use of 100 mg entrectinib in volunteers with impaired hepatic function. All volunteers will be resident in the study center and remain under medical supervision following study drug administration and will undergo a standard battery of safety assessments. Hence, the risks to participants in this study are considered acceptable.

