#### **4.4.2 Contraception**

Women of childbearing potential must agree to remain abstinent (i.e. refrain from heterosexual intercourse) or use a highly-effective method of contraception (failure rate of <1% per year) throughout the study *and for 5 weeks after the last study treatment*.

Women must refrain from donating eggs during this same period. Examples of contraceptive methods with a failure rate of < 1% per year include bilateral tubal ligation, male sterilization, hormonal contraceptives that inhibit ovulation, hormone-releasing intrauterine devices, and copper intrauterine devices.

A woman is considered to be of childbearing potential if she is postmenarcheal but has not reached a postmenopausal state, and has not undergone surgical sterilization.

Postmenopausal is defined as at least 12 months without a period (i.e., amenorrhea) in a female at least 45 years of age and accompanied by a serum follicle-stimulating hormone [FSH] level judged by the Investigator to be consistent with postmenopausal status in the absence of a reversible medical iatrogenic cause. Surgically sterile is defined as permanently sterile via hysterectomy, bilateral oophorectomy, and/or bilateral salpingectomy by reported medical history and/or medical records.

*Men with female partners of child-bearing potential must agree to remain abstinent (i.e. refrain from heterosexual intercourse) or use *barrier* contraception throughout the study and for 3 months after the last study treatment. Men whose female partners are pregnant must also use barrier contraception throughout the study and for 3 months after the last study treatment to avoid potential exposure of the fetus to the study drug. All men must also refrain from donating sperm during the study and for 3 months after the last study treatment.*

Periodic abstinence (e.g., calendar, ovulation, symptothermal, or postovulation methods) and withdrawal are not acceptable methods of contraception.

For volunteers who are exclusively in same-sex relationships or are abstinent (when this is in line with the preferred and usual lifestyle of the volunteer), contraceptive requirements do not apply. If a volunteer who is in a same-sex relationship or abstinent at the time of signing the ICF becomes engaged in a heterosexual relationship, they must agree to use contraception, as described previously.

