#### **5.4.3.2      Pregnancies in Female Partners of Male Volunteers**

Male volunteers will be instructed through the Informed Consent Form to immediately inform the Investigator if their partner becomes pregnant during the study or within 28 days after the dose of study drug. A paper Clinical Trial Pregnancy Reporting Form should be completed and submitted to the Sponsor or its designee immediately (i.e., no more than 24 hours after learning of the pregnancy), either by faxing or by scanning and emailing the form using the fax number or email address provided to Investigators. Attempts should be made to collect and report details of the course and outcome of any pregnancy in the partner of a male volunteer exposed to study drug. When permitted by the site, the pregnant partner would need to sign an Authorization for Use and Disclosure of Pregnancy Health Information to allow for follow-up on her pregnancy. If the authorization has been signed, the Investigator should submit a Clinical Trial Pregnancy Reporting Form when updated information on the course and outcome of the pregnancy becomes available. An Investigator who is contacted by the male volunteer or his pregnant partner may provide information on the risks of the pregnancy and the possible effects on the fetus, to support an informed decision in cooperation with the treating physician and/or obstetrician.

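### Volunteers are asked to notify a pregnancy only up to 28 days after the dose, although the protocol's contraception period runs 5 weeks for women and 3 months for men

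*Combined protocol and SAP*

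**What the plan says.** **Notification.** Section 5.4.3.1 instructs women of childbearing potential to tell the Investigator at once "if they become pregnant during the study or within 28 days after the dose of study drug". Section 5.4.3.2 instructs men, through the consent form, to do so "if their partner becomes pregnant during the study or within 28 days after the dose of study drug".

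**Contraception.** Section 4.4.2 requires women to use highly effective contraception or remain abstinent throughout the study "and for 5 weeks after the last study treatment". Men with partners of childbearing potential must remain abstinent or use barrier "contraception throughout the study and for 3 months after the last study treatment". The synopsis and Section 1.2.2 give the same durations.

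**Reason for the contraception period.** Section 1.2.2 states: "Potential risks to a developing fetus from entrectinib exposure in utero are addressed by" excluding pregnant women and requiring contraception. The Version 2 amendment rationale describes the contraception update, including barrier use by men with pregnant partners "to avoid potential exposure of the fetus to the study drug (Sections 1.2.2 and 4.4.2". It does not list Section 5.4.3.

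**Once the site knows.** Section 5.4 includes pregnancies among the events that the Investigator must report within 24 hours of learning of them, and sets no end date of its own. Section 5.4.3.2 asks for attempts to collect the course and outcome of "any pregnancy in the partner of a male volunteer exposed to study drug". Sections 5.4.3.3 and 5.4.3.4 class abortions and birth defects as serious adverse events.

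**The concern.** The protocol sets its own period for managing fetal exposure and then stops asking volunteers about pregnancy before that period ends. A woman who conceives in week 5, or a man whose partner conceives in month 2 or 3, is inside the contraception period but has no protocol instruction to tell the site. If the pregnancy is otherwise uneventful, it may never be notified and so not be followed to outcome.

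The amendment history suggests that the sections were not aligned, because the contraception update is listed for Sections 1.2.2 and 4.4.2 only. It does not prove an oversight: the rationale also mentions unlisted minor changes and does not give the Version 1 periods.

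**Working it through.** The plan gives no figure to reproduce. The check is date arithmetic plus two rough scale calculations.

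**Inputs**
- Notification limit: 28 days after the dose (Sections 5.4.3.1 and 5.4.3.2).
- Contraception period: 5 weeks for women, 3 months for men (Section 4.4.2). Three calendar months are 89 to 92 days, depending on the start date.
- One dose per volunteer (Section 4.3.2), so both periods start on the same day.
- Last scheduled contact: 11 to 13 days after dosing (Section 3.2). The last pregnancy test is at that visit (Section 4.5.5.3, Appendix 1).
- End of study: last scheduled procedure of the last volunteer (Section 3.2). Controls are enrolled after all impaired volunteers have been dosed (Section 3.1).

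**Gap = contraception period − notification limit**
- Women: 5 × 7 − 28 = 7 days; 7/35 = 20%.
- Partners of men: 89 − 28 = 61 days, 61/89 = 68.5%; 92 − 28 = 64 days, 64/92 = 69.6%.

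**Does the reference to the study period close the gap?** If it means the individual's own participation, it ends at 11–13 days and 28 days is the operative limit. If it means the whole trial, let d be the days from a volunteer's dose to the last dose in the trial. Cover after the volunteer's own dose is then max(28, d + 11 to 13) days.
- The full gap remains if d + 13 ≤ 28 or d + 11 ≤ 28, that is, d up to 15 to 17 days.
- Some gap remains for women if d < 35 − 13 = 22 to 35 − 11 = 24 days.
- Some gap remains for men if d < 89 − 13 = 76 to 92 − 11 = 81 days.

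This reading therefore helps volunteers dosed early. It does not help those dosed last, who are the controls.

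**Expected pregnancies in the women's gap.** Assume all 24 planned volunteers are women of childbearing potential, each at the 1% per year failure limit in Section 4.4.2: 24 × 0.01 × 7/365 = 0.0046. The figure grows in proportion if more than 24 are enrolled, and it assumes that the method is used as required. The documents give no failure rate for barrier methods, so no figure is offered for men's partners.

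**Residual drug at Day 28 (28 × 24 = 672 h).** Fraction left = 0.5^(672/half-life), with half-lives from Table 2:

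| Analyte | Condition | Half-life (h) | Fraction left |
|---|---|---|---|
| Entrectinib | with itraconazole | 49.8 | 0.0087% |
| M5 | with itraconazole | 88.0 | 0.50% |
| Entrectinib | alone | 20.2 | 9.7 × 10⁻⁹ % |
| M5 | alone | 40.8 | 0.0011% |

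The itraconazole rows are the relevant upper case, because Section 3.3.1 expects severe impairment to act on exposure much as that inhibitor does. The M5 rows are approximate, since M5 is formed over time and does not simply decay from the moment of dosing.

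**The case against.** The two periods need not be equal. Contraception carries a precautionary margin, whereas 28 days is the single safety window used throughout Section 5 for adverse events, serious adverse events and events of special interest. No statement in the protocol requires the notification and contraception periods to match.

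Several rules also reach beyond Day 28. The entry in Section 5.4, "Pregnancies (see Section 5.4.3 for details on reporting requirements", has no end date there, details are sought for any partner pregnancy, abortions and birth defects are serious adverse events, and Section 5.6 covers later related serious events. Men are instructed through the consent form, which was not available and might carry a longer period. The consequence is in any case slight.

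Much of this stands. It limits the gap to volunteer notification of an uneventful pregnancy, and it keeps the point minor. It does not remove the point. Each of those rules acts only once the site knows, and no visit or test is scheduled after Day 12–14. Agreement with the adverse event window also does not explain why notification should stop inside the period that the protocol manages for fetal exposure.

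**Conclusion.** The mismatch is real in the protocol text: up to 7 of 35 days (20%) for women and up to 61–64 of 89–92 days (69–70%) for partners of men have no volunteer-notification instruction. A trial-level reading of the study period reduces this for volunteers dosed early but leaves it in full for those dosed within 15–17 days of the last dose.

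The practical effect is small. About 0.005 pregnancies would be expected in the women's gap under the assumptions shown, residual drug at Day 28 is very low, and Section 1.1.2 reports entrectinib as neither mutagenic nor clastogenic. The pharmacokinetic endpoints are unaffected.

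Confidence is high for the wording mismatch. Whether a pregnancy would in practice go unnotified also depends on the consent form. Severity: minor.

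**What to change.** In Section 5.4.3.1 replace the 28-day limit with 5 weeks after the dose. In Section 5.4.3.2 replace it with 3 months after the dose. If the consent form carries the 28-day limit, change it to match.

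The cost is a minor wording amendment and slightly longer passive follow-up. No visit, test or call is added, and dose, pharmacokinetic sampling and sample size stay as they are. Notification would still rely on the volunteer, but the instruction would then last as long as the contraception requirement.
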